#### **7.4.6.2 Physical examination**

Physical examination will be performed which must comprise a neurological examination.

Significant findings made after the start of study drug which meet the definition of an Adverse Event must be recorded.

#### **7.4.6.3 ECG**

A standard 12 lead ECG is to be performed during screening and significant findings must be recorded.

#### **7.4.6.4 Performance status**

Performance status (PS) will be assessed using the Karnofsky scale for patients >16 years and Lansky scale for patients ≤16 years of age. Note: Patients who are unable to walk because of paralysis, but who are up in a wheelchair, will be considered ambulatory for the purpose of assessing the performance score.

#### **7.4.6.5 Drug levels and pharmacokinetic assessments**

None.

#### **7.4.6.6 NFTI-QOL (Neurofibromatosis 2 Impact on Quality of Life)**

At Baseline, 6-months, and off-study, adult subjects (≥18 years of age) will be asked to complete the validated NFTI-QOL, to assess the impact of their disease on their ability to perform activities of daily life. The questionnaire has not been validated in pediatric NF2 patients.

#### **7.4.6.7 MRI and audiogram**

MRI (including volumetrics) and audiogram, i.e. efficacy assessments, will be obtained at baseline and after every 3rd cycle, as previously described and outlined in Section 7.4.1.

## **8 Protocol Amendments, or Changes in Study Conduct**

Any change or addition (excluding administrative) to this protocol requires a written protocol amendment that must be reviewed by Pfizer and the investigator before implementation. Amendments significantly affecting the safety of subjects, the scope of the investigation or the scientific quality of the study require additional approval by the IRB. A copy of the written approval of the IRB must be provided to Pfizer. Examples of amendments requiring such approval are:

1. increases in drug dose or duration of exposure of subjects,
2. significant changes in the study design (e.g. addition or deletion of a control group),
3. increases in the number of invasive procedures,
4. addition or deletion of a test procedure required for monitoring of safety.

These requirements for approval should in no way prevent any immediate action from being taken by the investigator or by Pfizer in the interests of preserving the safety of all patients included in the trial. If an immediate change to the protocol is felt to be necessary by the investigator and is implemented for safety reasons, Pfizer must be notified and the IRB at the center must be informed immediately. Amendments affecting only administrative aspects of the study do not require formal protocol amendments or IRB approval but the IRB must be kept informed of such administrative changes.

Examples of administrative changes not requiring formal protocol amendments and IRB approval include:

1. changes in the staff used to monitor trials
2. minor changes in the packaging or labeling of study drug

## **9 Description of the Informed Consent/Assent Process**

Patients will be recruited by physicians at NYULMC and approved study sub-sites. Consenting will take place under the direct supervision of the PI or one of the approved study co-investigators. Prospective subjects will receive detailed information about this study and its investigational nature. They will also be informed about risks and potential benefits of the study. All questions will be answered by the PI or one of the approved study co-investigators. All patients (or their legal guardian for pediatric patients, as applicable) will sign an IRB-approved informed consent detailing the patient's protection of human subjects involved in clinical trials. In addition, assent will be sought from pediatric patients  $\geq 7$  years of age. All subjects will receive a copy of their signed consent/assent form. The IRB-approved informed consent document will also be signed by one of the approved study investigators. This process as well as patient eligibility will be documented in the medical record. This study will be conducted in accordance with the Declaration of Helsinki and in compliance with all applicable laws and regulations of the locale where the study is conducted.

It is the responsibility of the PI and study investigators that the patient is made aware and consent is given that personal information may be scrutinized during audits by competent authorities and properly authorized persons, but that personal information will be treated as strictly confidential and not be publicly available. The investigator is responsible for the retention of the patient log and patient records.

## **10 Withdrawal from the Protocol**

Volunteers may discontinue participation in the study at any time without penalty or loss of benefits to which the volunteer is otherwise entitled.

If a patient decides to withdraw his/her consent, we will ask that he/she contact [name] and let her know that he/she is withdrawing from the study. Her mailing address is [name]. If he/she wishes to withdraw his/her Authorization as well he/she must contact [name] in writing.

Remember that withdrawing Authorization only affects uses and sharing of information after the subject's written request has been received, and he/she may not withdraw his/her Authorization for uses or disclosures that we have previously made or must continue to make to complete analyses or report data from the research

## **11 Data Management and Collection**

The investigators will record all information required by the protocol.

### **11.1 Confidentiality**

Each subject enrolled will, from that point forward, be identified by a unique identifier (subject number). This subject number will also be used for research specimens collected and shipped to analysts outside of the study sites. All records generated will be stored in a locked office area, only accessible to study personnel. Clinical information will be accessed, according to HIPAA requirements, by study personnel to complete study documents, as needed.

Only the PI and the study coordinator will have access to the log linking the subject number to the patient name, birth date and medical record number. The log will be kept in a locked drawer in the study coordinator's office. A secure password-protected computer file will be generated as well.

Medical records will be kept in accordance with state and federal laws concerning the privacy and confidentiality of medical information. Each participant in this research study may be asked to sign a separate informed consent document for specific procedures or treatment, and that informed consent form may be included in the medical record of that facility. The confidentiality of each volunteer's medical record is also protected by federal privacy regulations, as described below.

Study records include information that identifies the patient and that is kept in research files. All efforts will be made to keep this information confidential, but it cannot be guaranteed. If data from this study are to be published or presented, all information that identifies the patient will be first taken out. Volunteers will be informed of all protected health information used in this study. The consent form will seek written permission from the participant to use and disclose the following information for this research. The volunteer is required to sign this form. This Authorization will not expire unless the volunteer withdraws it in writing. The volunteer has the right to withdraw authorization at any time, except to the extent that NYULMC has already relied upon it or must continue to use the information to complete data analysis or to report data for this study.

## **12 Data Monitoring**

### **12.1 Monitoring Plan**

An internal Data and Safety Monitoring Committee (DSMC) of the NYUCI is the monitoring board for this study. The committee will review safety at scheduled intervals (not less than once/year) and at the time of planned interim analyses according to the NYUCI DSMC Charter. As described further in the "Statistical Methods" section of this protocol, an interim analysis will be done after stage 1 is completed (9 evaluable patients have been enrolled).

## 12.2 Stopping Rules

If safety concerns arise, the DSMC will identify these concerns and recommend modification or termination of the clinical trial. As described further in the “Statistical Methods” section of this protocol, if the number of responses is  $<1$  after the first stage is completed, axitinib will be deemed ineffective and the trial terminated. Recruitment will be halted after the 9th evaluable patient is enrolled (stage 1) until at least one response is observed.

## 13 Statistical Methods

To evaluate efficacy, radiographic response is treated as a binary variable whereby patients who achieve either a CR or a PR in any of the target tumors at any point within 12 months from beginning of therapy are considered responders and all others nonresponders.. A 2-stage Simon design will be used. Axitinib will be considered not of sufficient interest for further evaluation if the true response rate is 5% ( $p_0$ ) or less and considered active if the true response rate is 25% or greater ( $p_1$ ). With beta (probability of rejecting axitinib with true response rate 5%) set at 0.2 and alpha (probability of failing to reject a treatment with response probability of 25%) set at 0.05, the required sample size is 9 patients for stage 1 and an additional 8 patients for stage 2. If there are no responses after the first stage is completed, axitinib will be deemed ineffective and the trial terminated. Recruitment will be halted after the 9th evaluable patient is enrolled (stage 1) until at least one response is observed during the first 12 cycles. Axitinib will be considered effective and of interest for further study if after successful completion of both stages, the cumulative number of responses is  $\geq 3$ . Using this 2-stage design, the probability of early termination is 0.63 if the true response rate to axitinib is 5%.

Stage	Cumulative number of patients with radiographic responses	Decision
Stage 1: enter 9 patients	0	Terminate the trial: agent ineffective
	1 or more	Inconclusive result: continue trial (proceed to Stage 2)
Stage 2: enter 8 additional patients	2 or less	Terminate the trial: agent ineffective
	3 or more	Terminate the trial: agent effective

Disease and patient characteristics at baseline will be summarized using descriptive statistics. For qualitative variables, frequency distributions and proportions will be provided; for quantitative variables, summary statistics (e.g., mean, median, quartiles, standard deviations, etc.) and graphical displays (e.g., boxplots). Overall response rates will be estimated upon completion of the study along with exact 95% confidence intervals.

Secondary endpoints: Audiologic responses will be summarized over time using descriptive statistics and graphical displays. Similarly, quality of life will be summarized over time in these patients.

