## 3 Research Strategy

**Primary Objective:** To estimate the objective volumetric response rates to axitinib in pediatric and adult NF2 patients with VS.

**Secondary Objectives:** To assess the toxicity of axitinib given daily in patients with NF2 and to examine the association of objective measures of response on MRI, i.e. volumetric tumor analysis with clinical measures of response, i.e. (audiogram), as well as quality of life assessments (NFTI-QOL). In addition, response in non-VS tumors, such as other schwannomas and meningiomas, may be explored.

**Drug Dosage and Administration (adult patients, age  $\geq$ 18 years):** 5 mg axitinib PO BID, with increase to 7 mg PO BID and 10 mg BID after 2 and 4 weeks, respectively, provided no adverse reactions (i.e., not exceeding grade 2 toxicities) and normotensive and not receiving antihypertension medications. Axitinib will be given continuously in 28-day cycles.

**Drug Dosage and Administration (pediatric patients, age <18 years):** 2.4 mg/m^2 axitinib PO BID, with increase to 3.2 mg/m^2 PO BID after 2 weeks, provided no adverse reactions (i.e., not exceeding grade 2 toxicities) and normotensive and not receiving antihypertensive medications. Axitinib will be given continuously in 28-day cycles using a dosing nomogram shown in Section 7.3.1. The maximal dose of 3.2 mg/m^2 PO BID exceeds the recommended phase 2 dose from the pediatric phase 1 trial, with the rationale that young NF2 patients, who

are generally not pre-treated with myelotoxic chemotherapy are likely to tolerate a higher dose of axitinib compared to the heavily pre-treated, refractory cancer patients enrolled on the pediatric phase 1 study [J Clin Oncol 34, 2016 (suppl; abstr 10558)]. Similar to adult patients on this study, the option to escalate the dose is intended to optimize secondary target inhibition and therefore increase the likelihood of responses.

**Study Assessments:** MRIs including volumetrics and audiograms at baseline and after every 3rd cycle (i.e. 12 weeks). Monthly study visits including H&P, neurological examination and standard laboratory evaluations. Quality of life assessments (NFTI-QOL) at baseline and cycle 6.

**Treatment Duration:** Until radiographic progression or unacceptable toxicity.

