#### 5 Proposed Sample Size and Timeline for Recruitment

A maximum of 17 evaluable subjects will be accrued to this study. According to our initial estimates, and based on our prior experience with lapatinib and everolimus phase 2 trials for adults and children with an average accrual rate of  $>2$  patients per month, the expected accrual period was approximately 12 months. However, the widespread use of bevacizumab on clinical trials and off-label, has rendered a large number of NF2 patients ineligible for this study, resulting in slower than expected accrual. The protocol was amended to include pediatric patients after pediatric phase 1 data became available, to increase enrollment.

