## 7.2 Study Population

### 7.2.1 Patient population

Minimum of 9, maximum of 17 evaluable patients (based on observed volumetric responses, 2-stage study design, see Section 11)

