### **7.2.4 Monitoring of axitinib suspected toxicities**

Patients whose treatment is interrupted or permanently discontinued due to an adverse event or abnormal laboratory value suspected to be related to axitinib must be followed at least weekly until the adverse event or abnormal laboratory resolves or returns to grade 1. If a patient requires a dose delay of > 21 days from the intended day of the next scheduled dose, then the patient must be discontinued from the study.

All interruptions or changes to study drug administration must be recorded.

It will be documented whether or not each patient completed the clinical study. If for any patient either study treatment or observations were discontinued the reason will be recorded. Reasons that a patient may discontinue participation in a clinical study are considered to constitute one of the following:

1. adverse event(s)
2. abnormal laboratory value(s)
3. abnormal test procedure result(s)
4. disease progression
5. protocol violation
6. subject withdrew consent
7. lost to follow-up
8. administrative problems
9. death

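### Does leaving the term evaluable undefined put the two-stage go/no-go decision in doubt?

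*Combined protocol and SAP*

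**What the plan says.** The unit of counting is the evaluable patient throughout. Section 13 states "Recruitment will be halted after the 9th evaluable patient is enrolled (stage 1"), as do Sections 4 and 12.2. Section 12.1 says "an interim analysis will be done after stage 1 is completed (9 evaluable patients have been enrolled"). Section 5 says "A maximum of 17 evaluable subjects will be accrued to this study", and Section 7.2.1 gives "Minimum of 9, maximum of 17 evaluable patients (based on observed volumetric responses, 2-stage study design, see Section 11"). Section 11 is Data Management and Collection and has nothing on the subject.

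The classification rule is in Section 13. Patients with a complete or partial response in any target tumor within 12 months of starting therapy "are considered responders and all others nonresponders". The decision table in that section uses no qualifier: "Stage 1: enter 9 patients", then 8 more.

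On timing, Section 3 schedules "MRIs including volumetrics and audiograms at baseline and after every 3rd cycle (i.e. 12 weeks"). Section 7.2.4 says of a patient whose dose is delayed by more than 21 days: "then the patient must be discontinued from the study". Section 7.4.4 follows patients who stop for 30 days after the last dose, or longer if drug-related toxicity persists. The schedule in Section 7.4.1 lists no MRI for patients who stop early.

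**The concern.** An undefined term fixes the recruitment halt, the interim analysis and the maximum size. Two readings seem possible. Under reading A, every entered patient counts and one without a response MRI is a nonresponder. Under reading B, such a patient is not evaluable and is replaced. Sections 5 and 7.2.1 cap only evaluable patients, so reading B would leave total enrolment without a stated limit.

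The situation can arise. The first response MRI falls at about day 84. A patient whose last dose is before day 84 − 30 = 54, with no continuing toxicity, could leave follow-up unscanned. In an open-label, single-arm trial with a boundary of 3 in 17, one such patient could decide the result, and the choice of reading could be made after responses are known. The denominator of the final response rate and its exact interval would move with that choice.

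**Working it through.** **1. Reproduce the design.** Inputs from Section 13: 9 then 8 patients; stop at 0 of 9; effective at 3 or more of 17; null rate 5%, target 25%. With X the responses in stage 1,

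P(effective) = Σ over x ≥ 1 of P(X = x; 9, p) × P(at least 3 − x of 8; p), and P(stop early) = (1 − p)^9.

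- p = 0.05: early stop 0.95^9 = 0.630, the plan's 0.63. P(effective) = 0.2985 × 0.0572 + 0.0629 × 0.3366 + 0.0084 = 0.0466.
- p = 0.25: early stop 0.75^9 = 0.075. P(effective) = 0.2253 × 0.6329 + 0.3003 × 0.8999 + 0.3993 = 0.812.

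If every patient has a response MRI, the two readings coincide and these figures hold.

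**2. Assume a share d without a response MRI.** The documents give none. The values used are 1/16, 2/17 and 3/17 (6%, 12%, 18%). The first borrows the pediatric study in Section 1.1, where 1 of 16 eligible patients was inevaluable for toxicity, which is a different purpose and population. The other two are pure assumption.

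**3. Keep one definition of the response rate at a time.** If 5% and 25% are rates among scanned patients, reading A works at p(1 − d) and reading B at p. If they are rates among all treated patients (unscanned patients being nonresponders), A works at p and B at p/(1 − d).

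| Rate defined among | Quantity | Reading | d = 1/16 | 2/17 | 3/17 |
|---|---|---|---|---|---|
| Scanned | Type I error | A | 0.040 | 0.034 | 0.029 |
| Scanned | Type I error | B | 0.047 | 0.047 | 0.047 |
| Scanned | Power | A | 0.772 | 0.732 | 0.684 |
| Scanned | Power | B | 0.812 | 0.812 | 0.812 |
| All treated | Type I error | A | 0.047 | 0.047 | 0.047 |
| All treated | Type I error | B | 0.055 | 0.063 | 0.075 |
| All treated | Power | A | 0.812 | 0.812 | 0.812 |
| All treated | Power | B | 0.849 | 0.879 | 0.909 |

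With rates among scanned patients, the chance under A of a stage 1 stop at a 25% rate is 0.090, 0.106 and 0.126. Expected enrolment under B is 17/(1 − d) = 18.1, 19.3 and 20.6.

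**4. How often the readings disagree.** Any trial positive under A is also positive under B, because B keeps all of A's responders and can only add patients. The disagreement rate is therefore P(effective) under B minus that under A.

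- 25% among scanned: 0.812 − 0.772, − 0.732, − 0.684, that is 4%, 8%, 13%.
- 5% among scanned: 0.7%, 1.3%, 1.8%.
- 5% among all treated: 0.8%, 1.7%, 2.8%.

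**5. The estimate.** Take 3 responders and 20 treated, 3 of them unscanned. Using scanned patients only gives 3/17 = 17.6% (exact 95% CI 3.8% to 43.4%). Using all treated gives 3/20 = 15.0% (3.2% to 37.9%). The intervals largely overlap.

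**6. Which reading the text supports.** Section 13 puts everyone without a response among the nonresponders, and its table counts patients entered. Sections 4, 12.1, 12.2 and 13 count evaluable patients at enrolment. A status that needed a 12-week MRI could not be known then, so reading B would make the halt unworkable. No section mentions exclusion from analysis or replacement. Reading B rests only on the word itself and on the absence of a cap on total enrolment.

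**The case for a change.** The strongest reply is that if every entered patient counts, the word evaluable does no work, so its authors must have meant to leave someone out. The sentence classifying all others as nonresponders names no population and so cannot by itself say who fills the 9 and 17 places. A definition would cost one paragraph. Leaving it out lets the choice be made with responses in view, and the bias then runs one way, toward declaring the drug effective.

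Part of this stands. The term is undefined, the denominator of the final rate is not stated, and the reference in Section 7.2.1 to Section 11 is wrong. The rest is weaker. The word can naturally refer to patients who are eligible and start treatment, which is known at or near enrolment and leaves the halt usable. The route to an unscanned patient is partly inferred: Section 7.4.4 concerns safety follow-up, and Section 13 counts responses within 12 months of starting therapy without limiting them to time on treatment. Stops for progression depend on a measured enlargement, so unscanned patients would come mainly from toxicity or withdrawal. The wrong section number is a clerical slip and is no evidence about who is evaluable.

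**Conclusion.** The observation is accurate, but it does not call for a change to the plan. An analyst who applies Section 13 as written counts every entered patient, treats those without a response MRI as nonresponders, and uses the same set for both decisions and the interval. That is a sound and conservative rule. In the cases computed its type I error does not exceed 0.047, and any error is against the drug.

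The price is power: 0.77 to 0.68 instead of 0.81 if 6% to 18% have no response MRI and 25% of scanned patients respond. Replacement would keep 0.81 for about 1 to 4 extra patients (18.1 − 17 to 20.6 − 17), but would raise the type I error to between 0.055 and 0.075 if the 5% null refers to all treated patients. This is a fair trade-off on which neither choice is plainly better, and writing down the definition would mostly restate what Section 13 implies.

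All these sizes rest on assumed shares without an MRI. If every patient is scanned, the effect is zero. The disagreement of 4% to 13% applies only at a 25% rate among scanned patients; at 5% it is about 1% to 2% on that definition, and up to 2.8% if the 5% refers to all treated patients.

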## 6 Study Objectives

### Primary

- To estimate the volumetric response rates to axitinib in patients with NF2-related vestibular schwannomas (VS).

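### Minor: Section 13 does not say that its exact 95% interval allows for the stage 1 stop; read as Clopper-Pearson, its upper limit is too low at 1/17 and 2/17

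*Combined protocol and SAP*

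**What the plan says.** Both statements of the primary objective are about estimation: "To estimate the objective volumetric response rates to axitinib in pediatric and adult NF2 patients with VS" (Section 3) and "To estimate the volumetric response rates to axitinib" (Section 6).

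Section 13 sets the design: "A 2-stage Simon design will be used", and "the required sample size is 9 patients for stage 1 and an additional 8 patients for stage 2". On stopping it says: "If there are no responses after the first stage is completed, axitinib will be deemed ineffective and the trial terminated". The final rule reads "Axitinib will be considered effective and of interest for further study if after successful completion of both stages, the cumulative number of responses is" at least 3.

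The only planned interval is in the same section: "Overall response rates will be estimated upon completion of the study along with exact 95% confidence intervals". No method is named. Section 4 repeats the design without an interval. Sections 12.1 and 12.2 cover the interim analysis and the stopping rule only.

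**The concern.** A Clopper-Pearson interval on 17 patients assumes that 17 patients are always studied. Here they are not: a trial with no response among the first 9 ends there. The possible results are 0/9, or 1 to 17 responses among 17 with at least one in stage 1. An interval that ignores this uses the wrong sampling distribution, and the error is largest at the lowest counts.

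The affected results, 1/17 and 2/17, are trials that enrol in full and are then declared ineffective. For those, the upper limit is what readers use to judge how much activity has not been ruled out. A limit that is too low makes the negative result look firmer than it is.

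**Working it through.** **Inputs (Section 13).** Stage 1 has 9 patients, stage 2 has 8, total 17. Stop at 0/9; success at 3 or more of 17. Null rate 5%, target rate 25%. The interval is 95%, taken as 2.5% in each tail. Clopper-Pearson is the assumed reading of exact.

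**Distribution of the result under the design.** With true rate p:

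- P(0/9) = (1−p)^9
- P(s/17) = c(s) · p^s · (1−p)^(17−s), where c(s) = Σ C(9,x)·C(8,s−x) over x = 1 to 9

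This gives c(1) = 9 and c(2) = 9·8 + 36 = 108. A fixed sample of 17 would have 17 and 136, because it also counts the sequences with no response in stage 1.

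**The plan's own figures.** P(0/9) at 5% = 0.95^9 = 0.630, matching the stated 0.63. P(3 or more of 17) is 0.0466 at 5% and 0.812 at 25%. These meet the 0.05 and 80% targets with alpha and beta in their usual sense, so the count rule is sound.

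**Limits.** Results are ranked 0/9, 1/17, 2/17 and so on. Stage-wise ordering and ordering by observed rate agree here, since 0/9 is the only early stop. The two-stage upper limit at s is the p at which P(0/9) + P(1/17) + … + P(s/17) = 0.025. The lower limit is found in the same way from the upper tail.

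| Result | Clopper-Pearson | Two-stage exact | Rise in upper limit (points) |
|---|---|---|---|
| 0/9 | 0 to 33.6% | 0 to 33.6% | 0 |
| 1/17 | 0.1 to 28.7% | 0.3 to 34.7% | 6.0 |
| 2/17 | 1.5 to 36.4% | 1.6 to 38.5% | 2.0 |
| 3/17 | 3.8 to 43.4% | 3.9 to 44.0% | 0.6 |
| 4/17 | 6.8 to 49.9% | 6.9 to 50.0% | 0.15 |

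(Rises are computed before rounding.)

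**Tail probability at the Clopper-Pearson upper limit (nominal 2.5%).**

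- 1/17, p = 0.2869: (1−p)^9 + 9p(1−p)^16 = 0.0477 + 0.0115 = 0.0592
- 2/17, p = 0.3644: 0.0169 + 0.0023 + 108p²(1−p)^15 (= 0.0160) = 0.0353
- 3/17: 0.0279
- 4/17: 0.0257

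The two-stage limit restores the nominal value. At 1/17 with p = 0.3470, 0.0216 + 0.0034 = 0.0250.

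**How likely the affected results are.**

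| True rate | P(1/17) | P(2/17) | Either |
|---|---|---|---|
| 5% | 19.8% | 12.5% | 32% |
| 10% | 16.7% | 22.2% | 39% |
| 15% | 10.0% | 21.2% | 31% |
| 20% | 5.1% | 15.2% | 20% |
| 25% | 2.3% | 9.0% | 11% |

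**Coverage over all true rates (grid step 0.00002).**

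- Clopper-Pearson: minimum 94.8%, at p = 36.4%. It is below 95% only for true rates of 36.4–38.3% and 43.4–43.5%, about 2% of the range. The upper limit misses at most 3.5% of the time.
- Two-stage exact: minimum 95.0%. The upper limit misses at most 2.5% of the time.

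**The case against.** The strongest reply is that the text is unspecified rather than wrong: a two-stage exact interval is also exact, and the sponsor may intend one. That stands, and it is why the finding is conditional on the Clopper-Pearson reading. If a two-stage interval is intended, the change only records it.

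The second reply is that, judged by coverage, little is lost. At true rates of 5, 10, 15, 20 and 25% the two intervals have the same coverage (99.1, 97.8, 99.2, 98.9 and 98.8%), and neither upper limit ever falls below the truth. The shortfall appears only at true rates well above the 25% target. The 5.9% at 1/17 is also not the interval's error rate. It includes 0/9, whose own interval reaches 33.6% and still covers 28.7%; just above 28.7%, only 1/17 misses, with a chance of about 1.15%. All of this is correct and keeps the point minor. The chances of seeing 1/17 or 2/17 say how often the reported limit would differ, not how often it would exclude the truth.

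What the reply does not remove is that an interval described as exact 95% should hold its level under the design actually used, and this one does not quite. Nor does it explain why one response in 17 should carry a lower ceiling than none in 9.

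**Conclusion.** The point holds and is minor. Under the Clopper-Pearson reading, the upper limit is about 6.0 points too low at 1/17 and 2.0 points too low at 2/17. The gap is small at 3/17 and negligible from 4/17, and nothing changes at 0/9. No go/no-go decision is affected: the rule uses the count, both affected results are already classed as ineffective, and 25% lies inside both intervals in each case. That a 95% interval at 3/17 includes 5% is ordinary and is no part of this point.

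The conclusion assumes that the stage sizes are exactly 9 and 17 evaluable patients, that 0/9 is the only early stop, and that the interval is two-sided with 2.5% per tail.

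**What to change.** In Section 13, replace the interval sentence with wording such as:

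*At study end, the primary volumetric response rate will be estimated and given with an exact 95% confidence interval that accounts for the two-stage design (stage-wise ordering: 0/9 lowest, then 1/17, 2/17 and so on).*

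The current sentence speaks of response rates in the plural. If rates for other tumours will also carry intervals, state the method for those separately, because the stopping rule applies to the primary endpoint.

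The cost is one sentence and a few lines of code, with no change to sample size, decision rule or patient care. The drawback is a less familiar interval with higher upper limits at low counts: 6.0, 2.0 and 0.6 points at 1/17, 2/17 and 3/17. Fixing the method now also avoids choosing between two exact intervals once the result is known.
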